10.3 Analysis Population

All participants who are randomized and receive at least one IMR intervention will be included in the modified intention-to-treat (MITT) population.

10.4 Timing of Analyses

The final analysis will be performed when the last recruited patient has completed Visit 3 and after the finalization and approval of the statistical analysis plan document. The final analysis will be performed on blinded data transferred to the lead statistician following data cleaning conducted by a study research coordinator. Data cleaning will include checking for missing data/extreme values and outliers.

10.5 Missing Data

Missing at random will be judged based on tabulating missing Visit 3 primary outcome values by intervention group and demographic characteristics. If there is a substantial amount of missing data and missingness is considered to be not random, sensitivity analyses utilizing worst-case/baseline scenarios or imputation will be used for descriptive and inferential assessments to address attrition bias.

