3. OBJECTIVES AND OUTCOME MEASURES

Table 1 Objectives and Outcomes Measures			
Primary Objectives	Outcome Measures	Endpoints	Analysis
Demonstrate IMR as an acceptable add-on intervention in children with obesity.	1. completion of study Visit 3 (V3) 2. adherence to active IMR 3. participant satisfaction among active IMR participants	1. prevalence of completer status 2. prevalence of IMR completion (actual / planned reps over intervention period) in active IMR group 3. prevalence of agree or strongly agree to question of satisfaction with active IMR	Simple descriptive statistics: calculation of prevalence
Secondary Objectives	Outcome Measures	Endpoints	Analysis
Demonstrate changes in inspiratory muscle functioning and dyspnea reporting following IMR	1. Maximum inspiratory pressure (MIP) 2. Baseline Dyspnea Index score 3. MRC breathlessness scale	1. change in MIP over intervention period 2. change in dyspnea scores over intervention period	Analysis of covariance (ANCOVA)
Demonstrate changes in daily physical activity following IMR	1. moderate-vigorous physical activity (MVPA) time 2. sedentary physical activity (SPA) time 3. total steps	1. change in average daily MVPA time 2. change in average daily SPA time 3. change in average daily step count	Analysis of covariance (ANCOVA)
Exploratory Objectives	Outcome Measures	Endpoints	Analysis
Demonstrate changes in exercise capacity following IMR	1. heart rate during 3 minute step test	1. heart rate change during 3-minute step test	Analysis of covariance (ANCOVA)

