10.10 Efficacy Analyses

Aim 1: We will use exact 95% confidence intervals and Fisher's exact test to report and compare the expected satisfaction, adherence and SAE percentages within the IMR compared to the sham group.

Aim 2: We will use analysis of covariance (ANCOVA) to estimate and test the difference in mean 6-week change between treatment groups (IMR versus Sham) for each outcome adjusting for the baseline value of the outcome variable. Given the small sample size, sex (male/female), age, and BMI will each be evaluated in separate ANCOVA models. We will report adjusted (least squares) means with 95% confidence intervals (CI) for each group, as well as the estimated between-group difference in means with 95% CI and p-value for testing the null hypothesis of no difference between group means. The model assumptions will be verified for each outcome, and model fit will be assessed using residual plots.

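### Section 10.5 makes sensitivity analyses depend on a tabulation that cannot show whether data are missing at random and that does not look inside the secondary outcomes

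*Combined protocol and SAP*

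**What the plan says.** Section 10.5 gives the rule for deciding what kind of missingness is present: "Missing at random will be judged based on tabulating missing Visit 3 primary outcome values by intervention group and demographic characteristics". What follows depends on two conditions: "If there is a substantial amount of missing data and missingness is considered to be not random". Only then does the plan commit to "sensitivity analyses utilizing worst-case/baseline scenarios or imputation will be used for descriptive and inferential assessments to address attrition bias". It sets no threshold for a substantial amount and names no imputation method.

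Table 1 in section 3 lists the primary outcomes as "1. completion of study Visit 3 (V3) 2. adherence to active IMR 3. participant satisfaction among active IMR participants". The secondary outcomes are "1. Maximum inspiratory pressure (MIP) 2. Baseline Dyspnea Index score 3. MRC breathlessness scale" and "1. moderate-vigorous physical activity (MVPA) time 2. sedentary physical activity (SPA) time 3. total steps". Section 10.10 uses analysis of covariance (ANCOVA), adjusted for the baseline value, on the secondary outcomes to "estimate and test the difference in mean 6-week change between treatment groups". It does not say how children without a Visit 3 value are handled or what is assumed about them. Section 10.3 calls the analysis population modified intention-to-treat (MITT).

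**The concern.** Data are missing at random (MAR) if, given what was observed, the chance of being missing does not depend on the unseen value. They are missing not at random (MNAR) if it does. The distinction concerns values nobody has. A table of missingness by arm and demographics can show that loss is not completely random along those variables. It cannot go further and tell MAR from MNAR.

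The condition can therefore err both ways. It can be met when loss is related to arm or age in a way the model can handle. It can fail to be met when children with poor responses drop out but the counts happen to balance. In the second case the plan commits to no sensitivity analysis at all.

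Two further points follow. The table is built on primary outcomes, whereas the between-arm tests are on secondary ones. And one of the listed remedies, the baseline scenario, brings in its own bias when the outcome is expected to change in both arms.

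**Working it through.** **1. The plan's own attrition figure.** Table 5 is the only place where attrition enters a number. Two-sample t-test power, with noncentrality d×√(n/2), 2n−2 degrees of freedom and two-sided alpha 0.05, reproduces all 24 cells to within 0.0005. For d=0.75 and n=15 per arm, noncentrality is 0.75×√7.5 = 2.05 and power is 0.509, as printed. Table 5 stands. It treats attrition only as a smaller n and says nothing about bias.

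**2. Which outcomes the table can show as missing.**
- Visit 3 completion is always known.
- Adherence is logged by the device and app (section 4.3), not at Visit 3.
- Satisfaction is collected at Visit 3 (Table 4; section 6.2.3, Visit 3).
- Serious adverse events, added to Aim 1 in section 10.2, are collected from consent onward (section 8.5.1).

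Only satisfaction can be missing at Visit 3, so the table amounts to attendance. That is a fair proxy for missing inspiratory pressure or dyspnea scores in children who do not attend. It does not register gaps in children who do:
- Baseline Dyspnea Index answers W, X and Y carry no numeric grade (section 6.6.4).
- Follow-up activity needs seven full days of wear (sections 6.2.3 and 6.4), and there is no analysis rule for less.

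**3. Same table, different bias (illustration).** Assume 15 per arm, 3 missing in each arm (20%, the top of Table 5), change scores with SD 1, and 20,000 simulated trials. In the outcome-dependent case, active-arm loss is weighted by exp(−1.5 × standardised change) and sham loss is random. The table reads 3/15 versus 3/15 in every trial.

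| True difference | Loss | Available cases | Zero-change fill-in |
|---|---|---|---|
| 0.95 SD | completely random | 0.95 | 0.76 |
| 0.95 SD | outcome-dependent | 1.19 | 0.95 |
| 0 | completely random | 0.00 | 0.00 |
| 0 | outcome-dependent | 0.23 | 0.19 |

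The 0.95 in the second row arises because two opposite errors cancel under these particular settings. The last row shows that fill-in does not remove the bias.

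**4. Baseline scenario on pilot values.** Table 3 gives pre-exercise changes in maximal inspiratory pressure of +37.0 and +12.5 cmH2O, a difference of 24.5. If a fraction m is lost at random in both arms and set to no change, the difference becomes (1−m)×24.5. At Table 5's attrition levels:
- 6.7% (14/15 kept): 22.9
- 13.3% (13/15 kept): 21.2
- 20% (12/15 kept): 0.8×24.5 = 19.6

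The post-exercise difference is 14.6−(−19.0) = 33.6. At 20% loss it becomes 0.8×33.6 = 26.9.

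**5. Satisfaction.** Section 10.2 takes completers as the denominator, and the target in section 10.1 is more than 80%. Suppose 3 of 15 active-arm children are missing:
- 11/12 = 91.7% (exact 95% interval 61.5 to 99.8).
- Counting the missing as not satisfied, 11/15 = 73.3% (44.9 to 92.2).

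More generally, the completer target needs at least 10/12 (83.3%), while the best possible worst-case figure is 12/15 = 80%, which is not above 80%. With three missing, every result that meets the target among completers fails it in the worst case.

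**The case against.** The case on the other side has real substance.

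- **The secondary outcomes are not wholly ignored.** A reader might infer that they never enter the rule. That is too strong. Satisfaction is collected at the same visit as inspiratory pressure and dyspnea, so its absence stands in for theirs in non-attenders. Only gaps among attenders escape. Section 10.5 also applies the remedy to inferential assessments, section 10.7 promises a general look at missing data, and section 10.8 promises a CONSORT diagram with reasons for dropout. None of these changes the condition in section 10.5.
- **The fill-in does not replace the main result.** Section 10.5 calls these analyses sensitivity analyses and offers imputation as an alternative. The documents do not support reading this as a biased main estimate.
- **A near-halving of the effect is a special case.** Losing 5/15 active and 1/15 sham gives 37.0×10/15 − 12.5×14/15 = 13.0, or −47%. That needs a lopsided split at the highest attrition considered and the pre-exercise row. The post-exercise row gives 14.6×10/15 + 19.0×14/15 = 27.5, or −18%. The pilot itself had 10 of 11 complete all visits. Table 3 rests on 6 versus 5 children with asthma and a no-training control rather than sham.
- **No significance test is named.** One might object that a 5-versus-1 split gives only p=0.17 by Fisher's exact test. Section 10.5 speaks of tabulating and considering, so that figure describes a rule the plan does not contain.
- **Thirty children support only simple imputation models**, and a delta analysis has little to overturn where a comparison is already non-significant. It still shows how far the estimate and interval move.

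What survives is that the rule cannot establish what it claims to, and that the commitment to sensitivity analysis depends on it.

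**Conclusion.** The point holds, with moderate weight. The reasoning about MAR needs no figures: a tabulation by arm and demographics cannot establish it, whatever the sample size. The coverage gap is narrower than it first looks, being confined to attenders with ungraded dyspnea answers or short tracker wear. The documents give no basis for estimating how many there will be.

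The sizes are illustrations. The 24.5 to 19.6 cmH2O shrinkage assumes that the small asthma pilot's pre-exercise changes carry over and that loss is random at 20% in both arms. The 0.95 versus 1.19 SD contrast depends on the assumed dropout mechanism. The satisfaction result assumes 15 treated active-arm children with three missing. It matters most, because satisfaction is a primary outcome with a stated target.

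No power or sample-size figure changes. The study is a pilot, its primary endpoints are descriptive in Table 1, and section 10.6 calls it exploratory, so this does not threaten the trial as a whole.

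**What to change.** Rewrite section 10.5 along these lines:

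1. Tabulate missingness for every outcome by arm, with reasons, as description only. Include ungraded dyspnea answers and insufficient tracker wear. Remove the judgement of MAR and the condition attached to it.
2. State that the main ANCOVA uses all children with a Visit 3 value for that outcome and assumes MAR given arm and baseline value.
3. Whatever the table shows, report two further results for each ANCOVA outcome, in place of baseline fill-in. One is an imputation under MAR using arm, baseline value and device-recorded adherence. The other is a delta-adjusted analysis over a range fixed beforehand. Adherence is useful because it is recorded independently of Visit 3 attendance.
4. For satisfaction, always report the worst-case percentage beside the completer percentage. Missing children count as not satisfied, and all active-arm children in the MITT population form the denominator.

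The cost is SAP wording, a few lines of SAS and some extra sensitivity rows per outcome. No new data are needed. Section 10.4 places finalization of the SAP before the final analysis, so the wording belongs there.

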10.6 Multiple Testing

Adjustment for multiple testing will not be performed given the exploratory nature of this study.

10.7 General Summary of Study Data

Statistical analyses will be overseen by [name], a faculty member within the Department of Biostatistics & Bioinformatics at Duke. She will serve as the unblinded statistician and oversee the lead statistician.

Patient disposition, demographics, baseline measurements, outcomes and adverse events will be summarized overall and by intervention group. We will use standard summary statistics to describe the distribution of outcome measures outlined in each aim by intervention group including mean, standard deviation (SD), median, 25th and 75th percentiles (Q1-Q3) and range for continuous variables and frequency counts with percentages for non-missing data. We will assess distribution and normality assumptions, identify outliers, evaluate missing data and check for unusual patterns. We will use SAS version 9.4 or higher (SAS Institute, Inc., Cary NC) for all analyses, and a two-sided p-value <0.05 will be considered statistically significant. Data derivations, calculations and analysis programs will be archived to allow future replication of our results.

10.8 Subject Disposition

Some withdrawal from the study is expected for various reasons. A CONSORT diagram will be used to describe the number of patients that reached the various stages of the trial and the number of participants that dropped out and for what reasons.

10.9 Protocol Deviations

Protocol deviations are expected to be minimal and will be summarized in tables by randomized intervention group.

10.10 Efficacy Analyses

Aim 1: We will use exact 95% confidence intervals and Fisher's exact test to report and compare the expected satisfaction, adherence and SAE percentages within the IMR compared to the sham group.

Aim 2: We will use analysis of covariance (ANCOVA) to estimate and test the difference in mean 6-week change between treatment groups (IMR versus Sham) for each outcome adjusting for the baseline value of the outcome variable. Given the small sample size, sex (male/female), age, and BMI will each be evaluated in separate ANCOVA models. We will report adjusted (least squares) means with 95% confidence intervals (CI) for each group, as well as the estimated between-group difference in means with 95% CI and p-value for testing the null hypothesis of no difference between group means. The model assumptions will be verified for each outcome, and model fit will be assessed using residual plots.

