5.4. Treatment Assignment Procedures

5.4.1 Randomization procedures

Treatment assignment will be 1:1 (IMR or sham intervention), and will be obtained through the Duke REDCap randomization system using the randomization schedule as

designed by the unblinded statistician. All study staff and participants will be blinded to the treatment assignment with the exception of one un-blinded clinical research coordinator. Participants may be able to tell whether their device is set to the active resistance. Although complete masking may not be possible in all participants, participants will only be informed that they are receiving one of two resistances (low or active). However, all study staff that assess outcomes (and the lead statistician) will remain blinded. Participants will be instructed to not discuss their presumed IMR assignment with study staff.

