10. STATISTICAL CONSIDERATIONS

10.1 Study Hypotheses

Primary Specific Aims: Compare measures of satisfaction, adherence and safety between patients randomized to IMR as compared to sham to demonstrate IMR as an acceptable add-on intervention that promotes greater activity in children with obesity with no safety concerns. More satisfaction and adherence are expected in the IMR group compared to sham.

- Hypothesis 1: More than 80% of participants will be satisfied with active IMR at study completion.
- Hypothesis 2: Total active IMR adherence will be >80% of planned IMR repetitions.
- Hypothesis 3: Active IMR will not be associated with any serious adverse reactions.

Secondary Aim: Compare inspiratory strength (measured by mean change in MIP) in IMR versus sham participants to demonstrate changes in inspiratory muscle functioning and dyspnea following IMR. Also, to demonstrate changes in daily physical activity following IMR versus sham participants.

- Hypothesis 1: IMR will significantly increase inspiratory strength (measured by mean change in MIP) with more improvements in IMR compared to participants receiving sham.
- Hypothesis 2: IMR will reduce patient-reported dyspnea scores from activities of daily living and during the step test.
- Hypothesis 3: IMR will lead to reduced sedentary time, increased moderate-strenuous time and increased total daily activity measured by a wrist-worn continuous activity tracking monitor.

Exploratory Aim: Demonstrate changes in exercise capacity following IMR versus sham participants.

- Hypothesis 1: IMR will reduce the peak heart rate increase induced by the step test in IMR compared to sham participants.

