10.2 Objectives and Endpoints

Aim 1:

- Satisfaction with active IMR (yes/no) as an intervention rated at study completion measured as a percentage of study completers.
- Active IMR adherence measured as a percentage of planned IMR repetitions (completer status).
- Serious adverse events (yes/no) measured as a percentage of participants receiving at least one active IMR intervention.

Aim 2:

- Change in maximum inspiratory pressure as measured by maximal inspiration in centimeters of water.
- Change in dyspnea as measured retrospectively of activities of daily living.
- Change in sedentary time measured by mean daily sedentary time assessed by the Vivosmart 4 activity tracker.

- Change in moderate-strenuous physical activity time measured by the mean daily MVPA time assessed by the Vivosmart 4 activity tracker.
- Change in total daily activity measured by mean daily step count and mean daily calorie expenditure.

Aim 3:

- Change in heart rate during step test.

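### Section 10.10 compares satisfaction between arms with Fisher's exact test on a yes/no cut of an ordered item; a rank test on the full response would recover some power at almost no cost

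*Combined protocol and SAP*

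**What the plan says.** All references are to the combined protocol and SAP.

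- **The item.** Table 1 (section 3) defines the endpoint as "prevalence of agree or strongly agree to question of satisfaction with active IMR". The answers are therefore graded, with at least two grades of agreement. The number of grades is not given. Table 4 and the Visit 3 procedures schedule the questionnaire at Visit 3 without restricting it to one arm.
- **The coding.** Section 10.2 lists "Satisfaction with active IMR (yes/no) as an intervention rated at study completion measured as a percentage of study completers".
- **The hypothesis.** The numbered hypothesis in section 10.1 concerns one arm: "More than 80% of participants will be satisfied with active IMR at study completion". Table 1 gives the analysis of this objective as "Simple descriptive statistics: calculation of prevalence".
- **The comparison.** The primary aim in section 10.1 also sets out to compare satisfaction between IMR and sham, and gives a direction: "More satisfaction and adherence are expected in the IMR group compared to sham". Section 10.10 supplies the method: "We will use exact 95% confidence intervals and Fisher's exact test to report and compare the expected satisfaction, adherence and SAE percentages". Section 10.7 adds that "a two-sided p-value <0.05 will be considered statistically significant".
- **Size.** Allocation is 1:1 (section 5.4.1) with 15 per arm (sections 4.1 and 10.11). Table 5 gives power by Cohen's d. No power is given for satisfaction or for Fisher's test.

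**The concern.** The yes/no cut serves the one-arm hypothesis, which is about a percentage. The between-arm comparison does not need it. There the cut treats the two grades of agreement as equal and merges every grade below them, and Fisher's test then works well inside its nominal 5% at this sample size. For example, if 12 of 15 are satisfied on IMR, significance requires 5 of 15 or fewer on sham (p=0.025). At 6 of 15, an observed 80% against 40%, p is 0.060.

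What is at stake is modest. The plan states an expected direction and tests it with little chance of confirming it, although the answers needed for a more sensitive comparison are already on the questionnaire.

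**Working it through.** **1. The plan's own power table.** Two-sample t-test, two-sided 0.05, noncentrality d·√(n/2) with 2n−2 degrees of freedom. For d=0.75 and n=15 the noncentrality is 0.75·√7.5 = 2.05, and power is 0.509. For d=1.25 and n=15, power is 0.910. All 24 cells of Table 5 reproduce. The table is for a continuous outcome and is not tied to satisfaction, so it serves here only as a source of effect sizes.

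**2. Inputs for satisfaction.** From the documents: 15 per arm, two-sided 0.05, and 80% as the active-arm rate (the threshold in the hypothesis). Assumed, because the documents are silent: five response levels with IMR probabilities 0.02, 0.05, 0.13, 0.45 and 0.35 (the top two sum to 0.80), and sham obtained by moving a latent normal scale down by d. The sham percentage satisfied is then Φ(0.842 − d). At d=0.75 this is Φ(0.092) = 54%; at d=1.25 it is Φ(−0.408) = 34%.

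**3. Power.** Fisher and Pearson chi-square on the yes/no split come from summing the binomial probabilities of all 16×16 tables with p<0.05. Wilcoxon on the five levels comes from simulation (tie-corrected, continuity-corrected; 20,000 to 40,000 trials), so its last digit can move by a point or so.

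| d | Sham satisfied | Fisher, yes/no | Chi-square, yes/no | Wilcoxon, 5 levels | Wilcoxon minus Fisher |
|---|---|---|---|---|---|
| 0.25 | 72% | 0.03 | 0.08 | 0.09 | 6 points |
| 0.5 | 63% | 0.08 | 0.18 | 0.22 | 14 points |
| 0.75 | 54% | 0.19 | 0.35 | 0.44 | 25 points |
| 0.95 | 46% | 0.33 | 0.51 | 0.64 | 32 points |
| 1.15 | 38% | 0.50 | 0.67 | 0.80 | 31 points |
| 1.25 | 34% | 0.58 | 0.74 | 0.87 | 28 points |

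Across repeated runs and response distributions of this kind, the gain for d=0.75 to 1.25 was about 24 to 32 points.

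**4. Where the loss arises.** Chi-square and Fisher use the same split, so their difference is Fisher's conservatism: about 16 to 18 points for d=0.75 to 1.25. The rest, about 9 to 14 points, is the cut. Fisher's true size with 80% satisfied in both arms is about 1.7%.

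**5. Does the gain come from exceeding 5%?** No. A permutation version of the Wilcoxon test had size about 4% and power 0.45, 0.65, 0.81 and 0.86 at d=0.75, 0.95, 1.15 and 1.25.

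**6. Sensitivity.**
- Section 10.2 counts completers. At 12 per arm (20% attrition in Table 5) the gain for d=0.75 to 1.25 is about 20 to 27 points.
- If treatment moves children only across the agree cut, with the same spread within each side, the gain at 15 per arm over the same sham rates (54% to 34%) is about 4 to 7 points.
- Under a common odds ratio of 2 the gain is 10 to 13 points. With sham at 50% and an odds ratio of 4 (80% against 50%), power rises from 0.24 to 0.52. With most sham children also satisfied and an odds ratio of 5, gains are larger: 42 points at 70% and 51 at 80%.

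**The case against.** The strongest reply is that the numbered hypothesis is about one arm, Table 1 asks only for a prevalence, and a yes/no percentage is the right summary for that. The between-arm comparison rests on the opening of section 10.1 and one sentence of section 10.10. No decision rule uses its p-value. Section 10.6 calls the study exploratory, and section 10.11 warns about type II error in pilots. All of this stands and keeps the weight of the point low. It does not remove the comparison, which the plan states as part of the primary aim and tests at 0.05.

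A second reply also stands. Sham children use the same device on the same schedule under masking, so a gap of 26 to 46 percentage points (80% minus 54%, 80% minus 34%) may be optimistic. At d=0.25 or 0.5 the gain is smaller, and neither test is likely to detect the difference.

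A reader might infer three stronger things that the documents do not support:

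- That the plan loses 24 to 32 points as a matter of fact. That figure needs a response scale, a sham rate and an effect size that appear nowhere in the documents.
- That dichotomizing is the main cause. With 80% satisfied on IMR, more than half of the loss in the table above is Fisher's conservatism, which a less conservative test on the same percentages would also reduce.
- That the yes/no coding in section 10.2 is wrong or that the graded answers will be lost. The coding is needed for the 80% hypothesis, and nothing says that the graded answers will not be kept.

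**Conclusion.** The point holds as a minor one. For the between-arm comparison, Fisher's test on the cut is less powerful than a rank test on the full response in every scenario examined. How much less depends on assumptions that the documents leave open: with a five-level item, 80% satisfied on IMR, a general shift and 15 per arm, the loss runs from about 6 points at d=0.25 to 24 to 32 at d=0.75 to 1.25, and it is about 4 to 7 points if only the cut moves.

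The improvement does not rescue the comparison for smaller effects: Wilcoxon power is about 0.43 to 0.45 at d=0.75 and lower below that. Nor does it affect the pilot's main conclusion on acceptability, which rests on the active-arm percentages.

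**What to change.** - **Section 10.2:** keep the yes/no percentage, defined as in Table 1 (agree or strongly agree), and state the response levels of the item.
- **Section 10.10, hypothesis:** keep the percentage with its exact 95% confidence interval for the 80% hypothesis.
- **Section 10.10, comparison:** for satisfaction only, replace Fisher's test by an exact Wilcoxon rank-sum test on the full ordered response. Report the estimated probability that an IMR child rates higher than a sham child (ties counted as one half) with its 95% confidence interval.

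The cost is a few lines of SAP text and one more SAS procedure, with no new data or visits. Section 10.4 already requires the SAP to be final before the analysis, so the change can be made then. The small downside is an effect measure less familiar than a difference in percentages; the percentages would still be reported by arm.

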Together, we propose **BREATHE Fit**, a randomized SHAM-controlled 6-week trial of inspiratory muscle rehabilitation in children aged 8-17 years with obesity enrolled in the Duke HL. **Primary research question:** *Is IMR an acceptable add-on intervention that promotes greater activity in children with obesity?* The **BREATHE Fit** trial will address the following aims:

Aim 1. Demonstrate the acceptability of IMR in children with obesity.

Hypothesis 1a (H1a). More than 80% of participants will be satisfied with active IMR at study completion. H1b. Total IMR adherence will be >80% of planned active IMR repetitions. H1c. Active IMR will not be associated with any serious adverse reactions.

Aim 2. Demonstrate changes in inspiratory muscle functioning and dyspnea reporting following IMR. H2a. IMR will significantly increase inspiratory strength (measured by mean change in MIP). H2b. IMR will reduce patient-reported retrospective dyspnea scores during activities of daily living.

Aim 3. Demonstrate changes in daily physical activity following IMR.

H3a. IMR will lead to reduced sedentary time, increased moderate-strenuous time and increased total daily activity measured by a wrist-worn continuous activity tracking monitor.

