4.10 Study Definition of Completion

Participant study completion will be defined as a participant who has been enrolled and completes Visit 3.

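### Adherence is defined as a ratio of actual to planned repetitions, but 10.10 analyses it as a yes/no outcome with no per-child cut-off, so the planned interval and test do not address H1b

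*Combined protocol and SAP*

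**What the plan says.** The definitions all describe a ratio of repetitions:

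- Section 2.1, H1b: "Total IMR adherence will be >80% of planned active IMR repetitions". Section 10.1 repeats it: "Total active IMR adherence will be >80% of planned IMR repetitions".
- Table 1 (Section 3) gives the endpoint as "prevalence of IMR completion (actual / planned reps over intervention period) in active IMR group". Its analysis column for the primary objective reads "Simple descriptive statistics: calculation of prevalence".
- Section 10.2: "Active IMR adherence measured as a percentage of planned IMR repetitions (completer status", the last two words being a bracketed tag that is not explained. Section 10.2 marks satisfaction and serious adverse events as yes/no, but not adherence.

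Section 10.10 treats the three alike. It plans exact intervals at the 95% level plus a Fisher test, worded as an "exact test to report and compare the expected satisfaction, adherence and SAE percentages within the IMR compared to the sham group". Section 10.1 also anticipates a difference between arms: "More satisfaction and adherence are expected in the IMR group compared to sham".

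Four other provisions bear on the point. Section 4.10 says "Participant study completion will be defined as a participant who has been enrolled and completes Visit 3". Section 10.3 puts every randomised child with at least one IMR intervention in the MITT population. Section 10.7 promises means, SDs and quantiles for the outcomes by arm. Section 4.8 reports that earlier adherence was 79.2% of prescribed repetitions in six participants.

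**The concern.** An exact binomial interval and Fisher's test need independent binary observations. Satisfaction and SAEs supply one per child. Adherence as defined does not, because it is a continuous ratio for each child. The 80% in H1b is a target for total repetitions and is nowhere used to classify a child as adherent.

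That leaves two readings of 10.10. In the first, children are classified by an unstated cut-off and counted, which gives a valid interval for a quantity other than H1b. In the second, repetitions are pooled as if independent, which is invalid because they are clustered within children.

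The completer tag adds a second uncertainty: whether children who stop early count, and with what denominator. Adherence is one of three primary outcome measures, and the only prior figure is within a point of the target. Choices left open now could therefore settle the answer later.

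**Working it through.** **The plan's own figure.** Table 5 is the only design calculation. A two-sample t-test with two-sided alpha 0.05 and 15/14/13/12 per arm reproduces all 24 cells within 0.0005 (for example 0.509 at d = 0.75, N = 30). It concerns a difference in means and gives nothing for adherence.

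**Inputs.** There are 15 children per arm (4.1). The schedule is 3 × 50 × 3 = 450 repetitions a week (7.1.1), so 450 × 6 = 2,700 per child over 6 weeks (2.1) and 2,700 × 15 = 40,500 per arm. The documents give no between-child SD; the 10 to 25 points used below is an assumption.

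**Reading 1: one yes/no value per child.** With equal planned doses, total adherence equals the mean of the per-child ratios.

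- Ten at 95% and five at 55%: mean = (10×95 + 5×55)/15 = 81.7%, SD 19.5. Half-width = t(0.975, 14) × 19.5/√15 = 10.8, so the CI is 70.9 to 92.5. The share above 80% is 10/15 = 66.7%, Clopper-Pearson 38.4 to 88.2.
- Twelve at 81% and three at 20%: mean = (12×81 + 3×20)/15 = 68.8%. The share above 80% is 12/15 = 80% (51.9 to 95.7). The disagreement now runs the other way.
- All fifteen at 81%: the share is 15/15 at an 80% cut and 0/15 at a 90% cut.
- If per-child values follow a beta distribution with true mean 85% (H1b true), the true share above 80% is 72% to 76% for SDs of 10 to 25.

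**Reading 2: pooled repetitions.** An observed 82% of 40,500 gives an exact CI of 81.6 to 82.4. With an SD of 20 points and the child as unit, it is 82 ± 11.1, or 70.9 to 93.1. In simulation with equal arms at 80%, a two-proportion test on pooled repetitions (nominal 5%) rejected in about 88% of trials at SD 10 and 94% at SD 20.

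**Early stoppers.** Suppose 13 children are at 85% and two stop after week 2, having done 85% of 900 = 765 repetitions each (765/2,700 = 28.3%). On the full schedule the mean is (13×85 + 2×28.3)/15 = 77.4%; among completers it is 85%. One stopper gives 81.2% and three give 73.7%. Two of 15 is the 13.3% attrition column of Table 5.

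**Visit timing.** A flat 2,700 would penalise permitted early visits. Table 4 gives day 40 to 56 for Visit 3, while the Visit 3 procedures in 6.2 allow day 42 ± 5, or up to 14 days away with PI approval. A fully adherent child whose training ends at Visit 3 would score 37/42 = 88% on day 37 and 28/42 = 67% on day 28.

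**Comparing arms.** Beta-binomial simulation, 15 per arm, assumed means 85% and 70%:

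| Power (%) at SD | 10 | 15 | 20 | 25 |
|---|---|---|---|---|
| Fisher, 70% cut | 52 | 28 | 18 | 15 |
| Fisher, 80% cut | 83 | 50 | 33 | 26 |
| Fisher, 90% cut | 66 | 63 | 50 | 43 |
| Wilcoxon rank-sum | 97 | 80 | 69 | 68 |
| Permutation test on means | 96 | 76 | 52 | 37 |

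**The case against.** The best defence is that this is a pilot and much of the need is already met. Section 10.7 would give each arm's mean and SD, so an estimate close to H1b would appear anyway. Table 1 and the MITT definition together lean towards counting early stoppers. Section 10.4 requires an approved SAP before the final analysis, which leaves time to define the variable. All of this stands, and it limits the harm. It does not repair 10.10, whose stated interval and test still attach to something other than the endpoint.

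Three stronger readings are tempting, and the documents do not support them.

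- A reader might infer that the completer tag in 10.2 contradicts 4.10. Section 4.10 defines study completion, and Table 1 lists completer status as a separate endpoint. The tag is unexplained, perhaps misplaced; that is ambiguity, not contradiction.
- A reader might infer that dichotomising always costs power. The table above shows otherwise: at SD 25 the test on means has 37% power, below Fisher's 43% at a 90% cut. Only the rank test leads throughout, and only under the assumed means and SDs. Between-arm power has no bearing on H1b itself, which is a one-arm statement.
- A reader might infer from 5.5.6 that replaced children drop out of the analysis. That section allows an additional enrolment and says nothing about exclusion.

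**Conclusion.** The point holds and should be fixed before the final analysis. The inference planned for a primary outcome does not match the endpoint as defined, and no per-child cut-off exists to make it workable. That conclusion depends on no assumed SD.

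Its size does depend on assumptions. In the worked example the two quantities differ by 15 points (81.7% against 66.7%) and fall on opposite sides of 80%. Two early stoppers among 15 can also move the estimate across 80%, though one does not in the same example. The earlier 79.2% comes from six participants in a different study population, so it shows only that a result near the target is plausible.

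This is not a fatal flaw. The device logs every repetition (4.3), so the correct quantity can be computed whatever 10.10 says.

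**What to change.** In 10.10, keep exact intervals and Fisher's test for satisfaction and SAEs only. For adherence:

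1. For each MITT child, divide logged repetitions by those planned over that child's scheduled intervention period (450 a week; 2,700 for 6 weeks). Children who stop early keep the full scheduled denominator. A Visit 3 held early within the permitted window shortens it. Reconcile the two statements of that window, and say how training after day 42 is handled.
2. State in advance whether all logged repetitions count or only those reaching the pressure target. Section 4.3 makes that distinction, and the target differs by arm. Cap each child at 100%.
3. Report the active-arm mean with a 95% CI that uses the child as the unit (t-based or bootstrap), beside the 80% target. With equal denominators and no child over plan, this mean is exactly the H1b ratio; otherwise the two differ.
4. Compare arms on the per-child ratio with an exact Wilcoxon rank-sum test, and show both arm means.
5. Remove the completer tag from the adherence bullet in 10.2, report Visit 3 completion separately, and make the Table 1 analysis entry agree with 10.10.

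The cost is wording. There are three statistical drawbacks. The interval is wide: half-width 5.5, 8.3, 11.1 and 13.8 points for assumed SDs of 10, 15, 20 and 25. Skew pulls t coverage below nominal, to 92–94% at a true mean of 80% and 89–94% at 85% in simulation. The rank test compares distributions rather than means. The 80% target remains a pilot yardstick: at a true mean of exactly 80%, the estimate exceeds it in roughly half of trials.
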